10.1 Data Collection

The data collection plan for this study is to utilize REDCap to capture all treatment, toxicity, efficacy, and adverse event data for all enrolled patients.

10.1.1 REDCap

REDCap (Research Electronic Data Capture) is a free data management software system that is fully supported by the Weill-Cornell Medical Center CTSC. It is a tool for the creation of customized, secure data management systems that include Web-based data-entry forms, reporting tools, and a full array of security features including user and group based privileges, authentication using institution LDAP system, with a full audit trail of data manipulation and export procedures. REDCap is maintained on CTSC-owned servers that are backed up nightly and support encrypted (SSL-based) connections. Nationally, the software is developed, enhanced and supported through a multi-institutional consortium led by the Vanderbilt University CTSA.

10.2 Regulatory Considerations

All protocol amendments and consent form modifications will be made by the Principal Investigator. *Bristol-Myers Squibb* will have the opportunity to review and approve the changes prior to submission of these changes to the local IRB.

11 Statistical Considerations

The primary endpoint of this study is response rate. The trial design is a single arm, single-center, Simon optimal two-stage design. Patients will be evaluated for response at 12 weeks (84 days \pm 7 days). Patients will be enrolled in two stages with 13 patients in the first stage, and potentially an additional 13 patients in the second stage. The decision to enroll patients into the second stage will depend on the number of responses observed in the first stage, as described below.

11.1 Sample Size/Accrual Rate

As mentioned, a Simon's two-stage optimal design [Simon, 1989] will be used. The null hypothesis that the true response rate is 20% will be tested against a one-sided alternative. If there are 3 or fewer responses in these 13 patients, the study will be stopped. Otherwise 13 additional patients will be accrued for a total of 26 patients. The null hypothesis will be rejected if 10 or more responses are observed in 26 patients. This design yields a one-sided type I error of 0.025 and power of 60% when the true response rate is 40%. The target sample size is 26 evaluable patients and up to 30 patients (4 extra patients) will be accrued to account for non-evaluable patients or patients who withdraw prior to evaluation.

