1.1 Primary Objectives

The primary objective of the study is to estimate the proportion of patients with systemic response at 12 weeks using IMWG criteria in patients with multiple myeloma when treated with immunotherapy and radiotherapy. Systemic response is defined as partial or complete best response within this time

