5.1 Schedule of Assessment

Procedure	Screening (Day 0)	C1D1 (±3 days)	C1D15 (±3 days)	Cycles 2-4		Cycles 5+	Cycles 5+	End of Study
				D1	D15	D1	D15	
Informed Consent	X							
Medical History	X	X		X		X	X	X
Physical Exam	X	X		X		X	X	X
Vital Signs + weight	X	X	X	X	X	X	X	X
Performance Status (ECOG)	X	X		X		X	X	X
Concomitant Medications	X	X	X	X	X	X	X	X
Second Primary Malignancy	X	X	X	X	X	X	X	X
Adverse Events Assessment	X	X	X	X	X	X	X	X
Bone Marrow Aspiration/Biopsy ^a	X ^a			X ^a		X ^a		X ^a
Biopsy of Targeted Lesion	X							
Radiologic bone imaging:								
PET/CT, MRI	X				X			X
CBC w/ plts & diff	X	X	X	X	X	X	X	X
CMP, Mg, Uric Acid, LDH	X	X	X	X	X	X	X	X
Serum or urine pregnancy test	X	X	X	X	X	X	X	X
TSH	X			X		X		
Beta 2 microglobulin	X			X				
Response Assessment								
Serum quantitative immunoglobulins	X	X		X		X		X
free light chains, SPEP & SIFE	X	X		X		X		X
24-Hour urine for urine total protein	X	X		X		X		X
UPEP & UIFE	X	X		X		X		X
TREATMENT								
Nivolumab Infusion ^c		X ^c	X ^c	X ^c	X ^c	X ^c	X ^c	
Radiation to Targeted Lesion ^b		X ^b						
RESEARCH PROCEDURES								
Stool Samples (before nivo infusion) ^d		X ^d			X ^d	X ^d		
Saliva Sample collection (before nivo)		X						

Foot notes:

- a. Bone marrow aspirate pre-nivolumab infusion on C2D1, C4D1, C7D1, C10D1 and Q 12 weeks thereafter and as needed to confirm CR
- b. One course of radiation (6GY x 5 fractions), with first radiation on D1 AFTER IV nivolumab
- c. All Infusions will have a ± 3 day window.
- d. Stool samples will be collected on Day1, end of Radiation, C4D1 and C7D1.

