11.3 Analysis of Endpoints

11.3.1 Analysis of Primary Endpoints

The primary analysis will be an evaluation of the response rate. The trial decision rules are to conclude the treatment strategy is not worth further evaluation if in the first evaluable 13 patients, there are 3 or fewer patients with a response. If in the first 13 evaluable patients, there is at least 4 patients with a response, an additional 13 evaluable patients will be enrolled. If in the first 26 evaluable patients, there are 10 or more responses are seen, it will be concluded that this treatment strategy is worth further evaluation (the null hypothesis will be rejected). If in the first 26 evaluable patients, 9 or fewer responses are observed, the treatment will not be recommended for further evaluation in this patient population. The response rate will be estimated with a one-sided 95% exact binomial procedure (66). Analyses will be performed in R (R Core Team, 2017).

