11.3.4 Reporting and Exclusions

11.3.5 Evaluation of toxicity

All patients will be evaluable for toxicity from the time of their first treatment with Investigational agent. A DLT will be defined as any grade 4 non-hematological toxicity or any toxicity that interrupts treatment for more than 6 weeks, treatment-related deaths, or grade 3 treatment-related non-hematological toxicities. Once 8 patients have been enrolled, we will use a continuous Bayesian toxicity stopping rule that will pause the study for review if the posterior probability that the DLT event rate is greater than 20% is $> 80\%$, using an uninformative prior of Beta(1,1). The trial will reviewed if 3 or more of the first 8 patients experience DLTs, or 4 or more of the first 9-12, or 5 or more of the first 13-16, 6 or more of the first 17-21, 7 or more of the first 22-25.

11.3.6 Evaluation of response.

All patients included in the study will be assessed for response to treatment if they have received at least 1 nivolumab infusion.

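### Sections 11.1 and 11.3.6 do not settle whether a dosed patient who leaves before a usable response assessment counts in the 13 and 26 on which the primary decision rests

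*Combined protocol and SAP*

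**What the plan says.** - **Decision rules (11.3.1).** Stage 1: "If in the first 13 evaluable patients, there is at least 4 patients with a response", the trial goes on. Final: "If in the first 26 evaluable patients, there are 10 or more responses are seen", the null is rejected. Both counts are of *evaluable* patients.
- **Accrual (11.1).** The target is 26 evaluable patients. Up to 4 more "will be accrued to account for non-evaluable patients or patients who withdraw prior to evaluation". The sentence does not separate dosed from undosed patients.
- **Time of evaluation (section 11, opening paragraph).** Week 12, that is day 84 with 7 days either side. Section 1.1 adds: "Systemic response is defined as partial or complete best response within this time".
- **Toxicity set (11.3.5).** "All patients will be evaluable for toxicity from the time of their first treatment with Investigational agent".
- **Response (11.3.6).** "All patients included in the study will be assessed for response to treatment if they have received at least 1 nivolumab infusion". The word *evaluable* is not used, and no outcome is assigned when no assessment exists.
- **Confirmation (9.1).** Every response category needs two consecutive assessments. The response is dated from the first of them.

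**The concern.** Take a patient who receives one infusion and withdraws in week 3 with no response labs after baseline. Under the literal words of 11.1, this patient withdrew before evaluation and one of the 4 extra places may fill the gap. Under 11.3.6 the patient stays in the response set, presumably as a non-responder, though the plan does not say so.

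The choice matters because the margins are single patients: 3 against 4 of 13 at stage 1, and 9 against 10 of 26 at the end. Patients who leave very early in a refractory population are plausibly non-responders, and replacing them would push the tested rate upward. In an open single-arm trial the team can also see responses accumulate, so a denominator left open can be settled after its effect is known.

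**Working it through.** **Inputs.** From 11.1 and 11.3.1: null rate 20%, alternative 40%, stop at 3 or fewer of 13, reject at 10 or more of 26, at most 30 accrued, stated one-sided type I error 0.025 and power 60%. The documents give no early-loss rate, so the share *d* of dosed patients lost before a usable assessment is an assumption, shown over a range.

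**Step 1: reproduce the plan.** P(reject) = Σ over x = 4 to 13 of P(Bin(13, p) = x) × P(Bin(13, p) ≥ 10 − x).

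At p = 0.20:
- x = 4: 0.1535 × 0.0300 = 0.0046
- x = 5: 0.0691 × 0.0991 = 0.0068
- x = 6: 0.0230 × 0.2527 = 0.0058
- x = 7: 0.0058 × 0.4983 = 0.0029
- x ≥ 8 together: 0.0010
- Sum: 0.0211

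At p = 0.40 the sum is 0.606. Power matches the stated 60%. The type I error lies under 0.025, as is usual for a discrete test with a nominal ceiling.

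**Step 2: replacement reading.** Assume that 20% is the rate among all dosed patients, and that every patient lost is a non-responder and is replaced. The rate among those counted is then 0.20/(1 − d); at d = 5% it is 0.20/0.95 = 0.2105. Applying the rules to the first 13 and first 26 not lost, with at most 30 dosed, gives:

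| Early loss d | Type I error |
|---|---|
| 0 | 0.021 |
| 2% | 0.024 |
| 2.5% | 0.025 |
| 5% | 0.029 |
| 10% | 0.034 to 0.039 |

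The range at 10% depends on whether a trial that ends with fewer than 26 evaluable among 30 (probability 0.175) can still reject. The chance of passing stage 1 under the null, P(Bin(13, p) ≥ 4), goes from 25.3% to 28.6% at 5% loss.

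**Step 3: how often the two denominators disagree** (first 26 not lost against first 26 dosed, same assumptions, short trials allowed to reject).
- True rate 20%: 0.3% of trials at 2% loss and 0.8% at 5%. This equals the rise in type I error: 0.0241 − 0.0211 = 0.0030 and 0.0294 − 0.0211 = 0.0083.
- True rate 40%: 3.1% and 7.8%. All of these are extra rejections under replacement: power goes from 0.606 to 0.637 and 0.684, and the differences are 0.031 and 0.078.

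**Step 4: dosed-patient reading.** If dosed patients without an assessment stay in as non-responders, and 40% is the rate among assessed patients only, the effective rate is 0.40 × (1 − d). At d = 2% this is 0.392 and power is 0.574. At d = 5% it is 0.38 and power is 0.525.

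**Step 5: who is exposed.** Response is the best response within 12 weeks. The calendar in 5.1 places the response labs ("Serum quantitative immunoglobulins", light chains, electrophoresis) on Day 1 of each cycle and at End of Study, and 6.4 speaks of assessments every 2 weeks. The unclear cases are therefore mainly patients who leave before C2D1, about 4 weeks in, without an End of Study visit.

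**The case against.** The best defence is that 11.3.6 is the definition. It follows 11.3.5 under the heading on reporting and exclusions (11.3.4, which has no text of its own) and gives for response the same kind of condition that 11.3.5 gives for toxicity. On that view the 4 extra places cover patients never dosed, and the phrase about withdrawal in 11.1 is loose wording about accrual. No sentence orders a dosed patient to be replaced. This is probably the intention, and it lowers both severity and confidence. It does not close the gap: 11.1 lists withdrawal before evaluation separately from being non-evaluable, evaluation is at week 12, and an instruction to assess does not say what to record when no assessment was made.

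The second defence is size. At 2% loss the type I error is still below 0.025, and any inflation needs two assumptions that the documents do not contain. That stands.

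A reader might also infer three stronger things:
- **That type I error could double to about 0.052.** That figure puts 0.20 × 30/26 = 0.2308 into the uncapped formula. With accrual capped at 30 and d = 4/30, the result is 0.045 if short trials can reject and 0.033 if they cannot. Nothing in the documents suggests that all 4 extra places would go to dosed non-responders.
- **That the disagreements at a true 40% rate are wrong conclusions.** Under the stated assumptions they are all correct rejections.
- **That the plan instructs replacement of dosed patients.** It only leaves room for it.

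**Conclusion.** The point holds as an inconsistency between 11.1 and 11.3.6 over the denominator of the primary rules, with 11.3.6 the likelier intention. The group affected is probably small. Type I error passes the stated 0.025 only above about 2.5% early loss, and only if the 20% null refers to all dosed patients and those lost are replaced non-responders. If loss is unrelated to response, or the null refers only to assessed patients, replacement causes no inflation. The documents do not support saying that the error rate is in fact exceeded. Minor to moderate severity, moderate confidence. It is worth correcting because the correction is cheap and the rules turn on one response.

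**What to change.** In 11.1 and 11.3.1:
1. State that response-evaluable means at least one nivolumab infusion, which is the plan's own 11.3.6 criterion.
2. Count every dosed patient without a documented partial response or better within 12 weeks as a non-responder.
3. State whether a first partial response by week 12 that is confirmed later counts. Section 9.1 dates response from the initial test but requires two consecutive assessments.
4. Use the 4 extra places only for registered patients never dosed.
5. Report the rate among patients with a response assessment as a sensitivity analysis.

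Settle this before responses are counted.

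**Cost.** No new patients or procedures. The reported rate may be slightly lower, and the allowance no longer covers withdrawals after dosing. The stated 60% power holds if 40% is the rate among dosed patients; if it applies only to assessed patients, power is about 57% at 2% loss and 53% at 5%. Defining evaluable as assessed, with a stated minimum assessment, would also remove the ambiguity, but it keeps the upward bias if early dropouts are non-responders.

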11.2 Stratification Factors

None

11.3 Analysis of Endpoints

11.3.1 Analysis of Primary Endpoints

The primary analysis will be an evaluation of the response rate. The trial decision rules are to conclude the treatment strategy is not worth further evaluation if in the first evaluable 13 patients, there are 3 or fewer patients with a response. If in the first 13 evaluable patients, there is at least 4 patients with a response, an additional 13 evaluable patients will be enrolled. If in the first 26 evaluable patients, there are 10 or more responses are seen, it will be concluded that this treatment strategy is worth further evaluation (the null hypothesis will be rejected). If in the first 26 evaluable patients, 9 or fewer responses are observed, the treatment will not be recommended for further evaluation in this patient population. The response rate will be estimated with a one-sided 95% exact binomial procedure (66). Analyses will be performed in R (R Core Team, 2017).

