11.3.2 Analysis of Secondary Endpoints

With adequate follow-up time, secondary endpoints of progression-free survival (PFS) and overall survival (OS) will be assessed by Kaplan-Meier survival analysis and 95% confidence intervals for median PFS/OS will be calculated using Greenwood's formula. PFS will be defined as the time from first treatment day until objective or symptomatic progression. OS will be defined as the time from first treatment day until death. The frequency of subjects experiencing toxicities will be tabulated. Toxicities will be assessed and graded according to CTCAE v. 4.0 terminology. Exact 95% confidence intervals around the toxicity proportions will be calculated to assess the precision of the obtained estimates.

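### The primary response rate gets only a one-sided 95% bound: looser than the one-sided 0.025 test, and with no second limit although the objective is estimation

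*Combined protocol and SAP*

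**What the plan says.** All references are to the combined protocol and SAP.

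- **Objective.** Section 1.1: "The primary objective of the study is to estimate the proportion of patients with systemic response at 12 weeks". The protocol summary also words the primary aim as estimation.
- **Test.** Section 11.1: "The null hypothesis that the true response rate is 20% will be tested against a one-sided alternative". Its stated operating characteristics are "This design yields a one-sided type I error of 0.025 and power of 60% when the true response rate is 40" per cent.
- **Decision rule.** At stage 1: "If there are 3 or fewer responses in these 13 patients, the study will be stopped". At the end: "The null hypothesis will be rejected if 10 or more responses are observed in 26 patients". Section 11.3.1 repeats the rule for failure: with "9 or fewer responses are observed, the treatment will not be recommended for further evaluation in this patient population".
- **Interval for the primary endpoint.** Section 11.3.1: "The response rate will be estimated with a one-sided 95% exact binomial procedure (66", where 66 is a citation. The sentence does not say whether the bound is a lower or an upper one, or whether it allows for the two-stage design. The reference list ends at 63.
- **Intervals for secondary endpoints.** Section 11.3.2: "Exact 95% confidence intervals around the toxicity proportions will be calculated to assess the precision of the obtained estimates". The same section plans 95% confidence intervals for median PFS and OS.

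**The concern.** A one-sided 95% bound leaves 5% in one tail. The limit that corresponds to a one-sided 0.025 test is the one-sided 97.5% bound, which is the lower end of a two-sided 95% interval. The plan gives no reason for the looser level.

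The bound has only one side. Section 11.1 rejects on high counts, so it is presumably the lower one. An objective worded as estimation needs both limits, and the plan provides fuller intervals for toxicity, PFS and OS than for its primary endpoint.

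Three things are at stake in the report:

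1. After a positive trial, the published lower limit sits further above 20% than a limit at the level of the test would.
2. After a negative trial, the planned analysis does not separate a result that excludes the 40% target from one that is merely inconclusive.
3. The word exact leaves the method open. One admissible reading produces a bound that excludes 20% for a result that the rule counts as a failure.

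**Working it through.** **Inputs** (sections 11.1 and 11.3.1): null rate 20%; target rate 40%; 13 patients in stage 1, stop at 3 or fewer responses; 26 in total, reject at 10 or more; test level one-sided 0.025; planned bound one-sided 95%.

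**1. Reproduce the design.** With X1 and X2 independent Bin(13, p), the probability of a positive trial is

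P(positive | p) = Σ over x = 4 to 13 of P(X1 = x) · P(X2 ≥ 10 − x).

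- p = 0.20: 0.0211, within the stated 0.025.
- p = 0.40: 0.606, matching the stated 60%. So 1 − 0.606 = 39.4% of trials end negative at the target rate.
- Probability of stopping at stage 1, P(X1 ≤ 3): 74.7% at p = 0.20 and 16.9% at p = 0.40.

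**2. Ordinary exact (Clopper-Pearson) limits.** With tail area a, the lower limit is the a-quantile of Beta(x, n − x + 1) and the upper limit is the (1 − a)-quantile of Beta(x + 1, n − x). The planned bound has a = 0.05; a two-sided 95% interval has a = 0.025 in each tail.

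| Result | Rule | Planned lower bound (a = 0.05) | Two-sided 95% interval |
|---|---|---|---|
| 3/13 | stop | 6.6% | 5.0% to 53.8% |
| 9/26 | fail | 19.4% | 17.2% to 55.7% |
| 10/26 | reject null | 22.6% | 20.2% to 59.4% |

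The planned lower bound at 10/26 is 22.6 − 20.2 = 2.4 points above the limit at the level of the test. Both lower limits fall below 20% at 9/26 and above it at 10/26, so both agree with the count rule.

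**3. What an upper limit would show after a negative trial** (two-sided 95% Clopper-Pearson upper limits):

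| 40% excluded | 40% not excluded |
|---|---|
| 0/13: 24.7% | 2/13: 45.4% |
| 1/13: 36.0% | 3/13: 53.8% |
| 4/26: 34.9% | 6/26: 43.7% |
| 5/26: 39.4% | 7/26: 47.8% |
| | 8/26: 51.8% |
| | 9/26: 55.7% |

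Summing the exact probabilities at a true rate of 40%, 37.9% of all trials end negative with 40% still inside the interval. That is nearly all of the 39.4% that end negative.

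**4. If exact means adjusted for the two stages.** Use stage-wise ordering, in which every stage 1 stop ranks below every result in 26 patients. The upper-tail probability of s responses in 26 is Σ over x = 4 to 13 of P(X1 = x) · P(X2 ≥ s − x). At p = 0.20 it is 0.0498 for s = 9 and 0.0211 for s = 10. Solving for the p at which this tail equals 0.05 gives a one-sided 95% lower bound of 20.02% at 9/26. That just excludes 20% for a failing result.

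At 0.025 per tail the two-sided limits are 17.75% to 57.4% at 9/26 and 20.5% to 60.1% at 10/26, which again agree with the count rule. The upper limits at 0/13 to 3/13 equal Clopper-Pearson. At 4/26 to 9/26 they are 53.8% or higher, so under this method 40% is not excluded at 4/26 or 5/26.

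**The case against.** **No decision changes.** Go/no-go is fixed by counts, nothing in the plan ties a conclusion to the bound, and the ordinary one-sided bound falls on the correct side of 20% at both 9/26 and 10/26. This stands. It limits the point to reporting.

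**A one-sided bound suits a one-sided test.** True, but the bound that matches this test is at 97.5%, and a one-sided bound at any level leaves the estimation objective half served.

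**A reader can compute the missing limit from the count.** Also true; no information is lost. Still, the primary analysis should state its own interval in advance and not leave readers to choose one afterwards, particularly as the methods can differ.

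**The conflict at 9/26 is remote.** It requires a two-stage adjustment that the text does not mention, and the margin is 0.02 points. It should carry little weight. It shows only that the method needs naming.

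**The direction and method may be in citation 66.** The supplied list stops at 63, so this cannot be checked. If an upper bound was meant, the lower limit is the one missing, and the same correction applies.

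**Conclusion.** The concern holds. The planned bound for the primary endpoint is at one-sided 0.05 while the test is at one-sided 0.025, and it supplies one limit where the objective calls for two.

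The missing upper limit matters more, because most failing counts are compatible with the 40% target and the design has only about 60% power there. The difference in level is smaller: about 2 points on the lower limit at 10/26. The decision rule and its error rates are untouched, so this is a change that should be made to the reported analysis, not a flaw in the design.

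The conclusion assumes that a lower bound is meant and that the denominators are 13 and 26 as planned. The conflict at 9/26 depends on the further assumption of a stage-wise adjusted bound.

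**What to change.** Replace the sentence in section 11.3.1 with one such as: the response rate will be reported as the observed proportion with a two-sided 95% exact confidence interval. Name the method in the same sentence and correct the citation.

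Two methods are reasonable. Coverage was found by enumerating every outcome of the two-stage design in 0.1-point steps for true rates from 5% to 95%.

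- **Clopper-Pearson** is the simplest. Its coverage is about 95% or higher for true rates of 20% to 50% (minimum 94.995%, at 48.2%) and falls to 94.3% at 55.7%. It is close to nominal but not guaranteed.
- **An interval from the two-stage sampling distribution** with stage-wise ordering keeps coverage at 95.3% or higher throughout. The ordering of outcomes must be stated.

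Either lower limit agrees with the count rule at the cut-off. The choice does affect whether 40% is excluded at 4/26 and 5/26, so it should be fixed before the data are seen.

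The cost is one sentence, plus one line of R for Clopper-Pearson or a short function for the two-stage interval. The reported lower limit at 10/26 falls from 22.6% to 20.2% or 20.5%. Sample size, decision rule and data collection do not change.
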